Fasted: Subjects should take nothing by mouth apart from water and other medications for at least 8 hours before drug administration and should continue fasting until at least 4

hours after administration of the morning dose. Subjects should be administered the drug product as a capsule or tablet (as indicated) with 200 mL (8 fluid ounces) of water. Water can be allowed, as desired, except for one hour before and after drug administration. All subjects will receive standardized meals at approximately 4- and 9- hours post dose. Additional details of the meals will be provided in the SRM.

Fed: Following an overnight fast (at least 8 hours), subjects should start the recommended high fat, high calorie breakfast 30 minutes prior to administration of the GSK3326595. Study subjects should eat this meal in 30 minutes or less; however, GSK3326595 should be administered 30 minutes after start of the meal. The GSK3326595 should be administered as a tablet with 200 mL (8 fluid ounces) of water. No food should be allowed for at least 2 hours post-dose. Water can be allowed, as desired, except for one hour before and after drug administration. All subjects will receive standardized meals at approximately 4- and 9- hours post dose. Further details of the meals will be provided in the SRM.

Any subject who experiences vomiting within 3 hours of dosing will be removed from the statistical analysis of PK comparability between tablet/capsule and tablet (fasted)/tablet (fed), and additional subjects will be enrolled to ensure 12 subjects complete all three periods.

As described in Section 8.2.2, the Day 4 (Period 2) visit may be performed on Day 4 or Day 5. The Day 8 (Period 3) visit (capsule administered in a fasting state) may be performed ± 1 day. Continuous daily dosing with GSK3326595 will only commence once the subject has completed the Period 3 visit, irrespective of whether that visit occurs ± 1 day.

If the GSK3326595 tablet bioavailability is comparable to that of the GSK3326595 capsules, all new and ongoing subjects may be switched from capsules to tablets for the remainder of the study, once they have been notified by the Sponsor.

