Survival Follow-Up ²⁰													Q6 months	

TMF-14123404

CONFIDENTIAL

- 1. If test performed within 3 months prior to first dose of study treatment, testing at screening may not be required. Discuss with Medical Monitor if unclear
- 2. See Section 8.3.1 for components of full and limited physical examinations
- 3. See Appendix 3 for definition of ECOG performance status
- 4. On serial PK days (Day 1 and Day 15), ECGs will be obtained at or about the time of PK sample collection, as described in the SRM. On other days, ECGs will be obtained predose.
- 5. If possible, DEXA to be performed on same machine for particular subject
- 6. Only if EOT is > 8 weeks from prior DEXA
- 7. Refer to Section 8.3.5 (Table 16) for complete listing of protocol-required laboratory assessments. Clinical labs performed during screening within 72 hours of first dose do not need to be repeated on Day 1. Folate and selected vitamins to be drawn at Screening, Week 4, Week 8, every 8 weeks thereafter and at EOT. If a subject's folate or selected vitamins result(s) remain borderline or low at EOT visit, further testing may be requested until no longer deemed necessary in the opinion of the Investigator and Medical Monitor.
- 8. Refer to Section 8.3.7 for description of components of ocular assessment. If a subject's ocular result(s) remain abnormal at EOT visit, further testing may be requested until no longer deemed necessary in the opinion of the Investigator and Medical Monitor.
- 9. On serial PK days (Day 1 and Day 15), subjects should fast from 8 hours prior to dose until 2 hours after dose. On all other days, GSK3326595 should be administered on an empty stomach at approximately the same time of day (± 4 h), with no food for 1 hour before and 2 hours after each dose. On serial PK days and for two days prior (Days 13 through 16), subjects should attempt to take GSK3326595 within a 1 hour window (i.e., 23-25 hours after the last dose).
- At each visit, the investigator should specifically ask the subject about any changes in vision since their last visit/contact (Section 9.2.2). The investigator should document the
 response, consider if there are any reported events which meet the definition of an AE or SAEs, and intervene as clinically appropriate following discussion with the Medical
 Monitor if necessary.

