- 8. Pre-dose urine samples will be collected near the time of dosing on Days 1 and 15 for PK and metabolite profiling. A separate container will be used to collect urine for PK and metabolite profiling from the time of dosing until 12h post-dose on days 1 and 15.
- 9. Refer to Section 8.2.1 for discussion of baseline biopsies. Tumor biopsies in the PK/PD expansion cohort are mandatory

Table 13 Time and Events for Food Effect and Relative Bioavailability Sub-Study

Food Effect and Relative Bioavailability Sub-Study (Section 4.2.6; samples collected in this section are in addition to any samples, studies, and visits described in Table 9)													
Procedure	Screening												
	_	D1	D2	D3	D4	D5	D6	D7	D8	D9	D10 and beyond		
Administer study drug ¹		Х			Х				Х	←====	============ \rightarrow^2		
Plasma PK samples ³		х	х		х	х			х	х	Refer to Table 9 for subsequent PK sample requirements		
Routine Clinical Laboratory Assessments (Refer to Table 9)	x	х							Х				

104

TMF-14123404

CONFIDENTIAL

NOTE: Subjects in the food effect and relative bioavailability sub-study are subject to all screening, safety, PK, and efficacy evaluations detailed in Table 9. Samples collected in this section are in addition to any samples collected in Table 9, with the exception of Day 1-9 PK collections, in which the time points in Table 13 supersede those in Table 9.

- Study drug should be administered in fed or fasted state, as capsules or tablets based on assignment as described in Section 4.2.6. At least 48 hours should separate each individual dose; in order to accommodate clinic schedules, the Day 4 visit may be performed up to one day late, and the Day 8 visit may be performed ±1 day (note that it may only be performed on Day 8 or Day 9 if the Day 4 visit is performed on Day 5, in order to allow the 48-hour window between doses). Refer to Section 8.2.2 for full discussion of visit windows.
- 2. Day 9 dose should be administered in clinic following collection of Day 8 24-hour timepoint PK sample.
- 3. PK samples following Day 1, Day 4, and Day 8 doses will be collected at Pre-dose (within 1 hour prior to dosing), 15m±5m, 30m±5m, 1h±5m, 2h±5m, 4h±10m, 6h±10m, 8h±15m, 12h±2h, 24h±2h and 30h±2h.

Table 14Time and Events for Part 2

Procedure	Screening	Days 1-21			Weeks 4 & 6	q8w (starting	q12w (starting	q26w (starting	EOT (within 30 days post-	Survival Follow-Up
		D1	D8	D15	D1	W8)	W12)	W26)	last dose)	i enen op
Screening		•	•			•	•			
Informed consent	Х									

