5.1.2. PK Analysis: Handling of excluded data after NCA (Non-Compartmental Analysis) analysis

When Clinical Pharmacology perform the NCA analysis they may, in some circumstances, elect to exclude certain data points from the analysis. These data points should also be excluded from summary statistics. A separate analysis dataset ADPCWNL will be generated by adding a flag for those records to be excluded. PK listings and individual PK figures will keep all the data, with listings indicated the records excluded from summary.

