Based on the US FDA guidance on food-effect bioavailability studies, the absence of a food-effect will be established if the 90% CI of the ratio for Cmax and AUC, based on log-transformed data, is within the 80 to 125% equivalence limit. Recommendation on the clinical significance of the effect of food will be based on the magnitude of the change and our understanding of the exposure-clinical response relationship.

For the evaluation of food effect, tmax at fed and fasted status will be presented by subject and dose cohort in tabular and graphical form.

Relative Bioavailability of Tablet

Pharmacokinetic (PK) parameters $AUC_{0-\infty}$ (or if not available AUC(0-t)) and Cmax will be log-transformed and analyzed using a mixed-effects model with formulation (tablet or capsule)sequence and period as fixed effects, and subject as a random effect. Point estimates and their associated 90% CIs will be constructed for the differences between between tablet and capsule. The point estimates and their associated 90% CIs will then be back transformed to provide point estimates and 90% CIs for the ratios of tablet (test) vs. capsule (reference) under fasted condition.

Code will be consistent with the above for food effect analysis. The analysis will exclude data for a given period if the subject did not receive the correct dose or formulation during that period.

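### Tablet/capsule comparison: the nominal 30-hour capsule sample falls about 6 hours after the next dose, and no SAP rule keeps it out of the capsule AUC

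*Protocol*

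**What the plan says.** The sub-study (Protocol 4.2.6, Table 2) has three single-dose periods. Periods 1 and 2 are tablets, fed and fasted in either order. Period 3 is the fasted capsule in both sequences. Doses in successive periods are at least 48 h apart.

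Note 3 of Protocol Table 13 sets one sampling schedule for the Day 1, Day 4 and Day 8 doses, ending "8h±15m, 12h±2h, 24h±2h and 30h±2h". Note 2 of the same table says "Day 9 dose should be administered in clinic following collection of Day 8 24-hour timepoint PK sample", and the table shows daily dosing from Day 9. Section 4.2.6 adds that "Continuous daily dosing with GSK3326595 will only commence once the subject has completed the Period 3 visit", without saying whether that visit includes the 30 h sample.

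SAP Table 13 runs AUC(0-t) to the last quantifiable concentration, with linear trapezoids while concentrations rise and log trapezoids while they fall. AUC(0-∞) adds the last concentration divided by λz. For tablet against capsule, SAP 9.2.2.2 takes AUC(0-∞), "or if not available AUC(0-t)) and Cmax will be log-transformed and analyzed using a mixed-effects model with formulation", with sequence and period also fitted. Tablet is the test and capsule the reference.

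The listed exclusions are a wrong dose or formulation (SAP 9.2.2.2) and vomiting within 3 h of dosing (Protocol 4.2.6). Otherwise, SAP 5.1.2 says of Clinical Pharmacology that "they may, in some circumstances, elect to exclude certain data points from the analysis".

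**The concern.** The intrusion affects only one side of the ratio. The tablet profiles are clean to 30 h because no dose follows within 48 h. Every capsule profile, in both sequences, is exposed. Because the capsule is given only in Period 3, the period term in the model cannot separate this artefact from a formulation effect.

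Other schedules in the protocol avoid the problem. The serial profiles in Table 9, and the Day 1 profiles in Tables 14 and 15, end with a sample marked as taken before the next dose. Table 13 has no such marking.

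Relative bioavailability is a stated secondary objective of Part 1. A finding of comparability lets the sponsor move all new and ongoing subjects to tablets (Protocol 4.2.6), and the SAP combines tablet and capsule cohorts within disease and dose (SAP 2.3.1, 5.1.1). A downward bias could make an equivalent tablet look low. It could also hide a tablet exposure that is truly higher.

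**Working it through.** The documents give no sample-size or precision figure for this comparison, so there is none to reproduce.

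**Timing.** With the Day 9 dose at the nominal 24 h, the gap to the 30 h sample is 30 − 24 = 6 h. If the dose directly follows the 24 h sample, the ±2 h windows give 28 − 26 = 2 h to 32 − 22 = 10 h.

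**Inputs.**
- Sampling at 0, 0.25, 0.5, 1, 2, 4, 6, 8, 12, 24 and 30 h (Protocol Table 13, note 3).
- Half-life 3 to 6 h (Protocol 7.1.3).
- Trapezoid rule from SAP Table 13.
- Assumed: one compartment, absorption rate ka 0.5 to 2 per hour, all samples quantifiable, identical formulations (true ratio 1.00), and a Day 9 dose equal to the capsule dose.

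**Formula**, in units of dose over volume: C(t) = ka/(ka − k) × (e^(−kt) − e^(−ka·t)), with k = ln 2 / half-life. The capsule's 30 h value gains C(6) from the Day 9 dose.

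**One case in full**, half-life 4.5 h and ka 1 per hour (k = 0.1540):
- C(24) = 0.0293; clean C(30) = 0.0116; C(6) = 0.4662. The capsule 30 h value is 0.0116 + 0.4662 = 0.4778.
- AUC(0-24) = 6.2345 for both formulations.
- Tablet, 24 to 30 h, falling: 6 × (0.0293 − 0.0116) / ln(0.0293/0.0116) ≈ 0.115. AUC(0-30) = 6.349.
- Capsule, 24 to 30 h, rising: 6 × (0.0293 + 0.4778)/2 = 1.521. AUC(0-30) = 7.756.
- Tablet/capsule = 6.349/7.756 = 0.819.

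**Ratio across the range:**

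| Half-life | ka 0.5 | ka 1 | ka 2 |
|---|---|---|---|
| 3 h | 0.791 | 0.815 | 0.834 |
| 4.5 h | 0.807 | 0.819 | 0.831 |
| 6 h | 0.823 | 0.830 | 0.839 |

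The capsule AUC(0-t) is thus inflated by 19% (1/0.839) to 26% (1/0.791). Its 30 h concentration is about 8 to 64 times its 24 h value, when it should be 0.25 to 0.5 times.

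**Windows** (ka 1.5, half-life 3 to 6 h, tablet at nominal times):
- 24 h sample and dose both at 26 h, last sample at 28 h: 0.86 to 0.92.
- Dose at 28 h, last sample at 30 h: 0.68 to 0.77.
- 24 h sample and dose both at 22 h, last sample at 32 h: 0.82 to 0.88.

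The size moves, but the ratio stays below 1.

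**AUC(0-∞).** If λz is fitted through the 30 h point (ka 0.7 to 3 per hour), the apparent half-life is 8 to 27 h, adjusted R² is about −0.2 to 0.16, and the ratio is 0.25 to 0.52. Such a fit would probably be rejected. The analysis would then fall back on AUC(0-t), which has the same problem.

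**After correction.** AUC(0-24) for both formulations gives 1.000, and AUC(0-∞) with λz from samples up to 24 h also gives 1.000. Dropping the point for capsule alone and then using AUC(0-t) compares 0–30 h with 0–24 h and gives 1.003 to 1.045. AUC(0-24) covers 91% to 99% of AUC(0-∞).

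**The case against.** The strongest reply is that the bias arises only if the 30 h value enters the non-compartmental analysis. That analysis is directed by the sponsor's clinical pharmacology group, uses actual sampling times, and follows working practices that are cited but not reproduced. SAP 5.1.2 allows points to be excluded, and SAP 9.2.2 runs these models only if profiles are well defined. A 30 h value many times the 24 h value would be obvious. This stands: the documents do not show that the reported ratio is wrong. They show that avoiding the error in every reference profile was left to undocumented discretion.

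The notes are also not strictly incompatible. Note 2 puts the dose after the 24 h sample, not immediately after it. With the ±4 h dosing window in Table 9 and the ±2 h sampling window, a sample at 28 h just before the dose would satisfy both. That is an extreme corner of the windows, not the nominal schedule.

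A reader might infer that an equivalent tablet would fail an 80–125% criterion. The documents do not support that. The limit is stated for food effect only, and comparability of tablet and capsule has no numeric definition. The width of the interval is also unknown. With 12 subjects and a ratio of 0.84, the lower 90% limit is 0.84 × exp(−1.796 × s × √(2/12)), where s = √ln(1 + CV²). This is about 0.81 at a within-subject CV of 5% and 0.78 at 10%.

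The half-life is a soft input. Protocol 7.1.3 gives 3 to 6 h without naming a species, beside animal bioavailability figures. Section 7.3.2 equates five half-lives plus 90 days with about 95 days, which read literally implies about 24 h. At 24 h the AUC(0-t) ratio is about 0.88 and AUC(0-24) covers only 47% to 49% of AUC(0-∞). The direction holds; the size and the cost of truncation change.

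**Conclusion.** The point holds as a gap in the plan. At nominal times the last capsule sample belongs to the next dose, the SAP's AUC rules run through it, and nothing requires its removal. If it is included, the tablet/capsule AUC ratio is biased down, to about 0.79 to 0.84 on AUC(0-t) for identical formulations. That size rests on a 3 to 6 h half-life, one-compartment kinetics, the assumed absorption rates and nominal times. The direction does not depend on those values.

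The scope is narrow. Cmax is unaffected. The food-effect comparison uses Periods 1 and 2 only and is untouched, as is the planned half-life comparison, which is fed against fasted. Capsule half-life matters only through AUC(0-∞). It would go too far to conclude that the completed Table 4.7 is biased, because the documents do not say how the sample was treated.

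This should be fixed, but it concerns a secondary pharmacokinetic objective and no primary endpoint. Confidence is high on timing and direction, and lower on size and on any effect on the switching decision.

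**What to change.** - In SAP 9.2.1 and 9.2.2.2, exclude from AUC and λz any Period 3 sample taken after the Day 9 dose.
- Compare tablet and capsule on the same window for both formulations: AUC(0-24), plus AUC(0-∞) with λz from samples up to 24 h where it can be estimated.
- SAP display Table 4.7 is marked as already produced. State how the Period 3 30 h sample was handled there, and rerun the table if the sample was included or the two formulations were integrated over different windows.
- Notes 2 and 3 of Protocol Table 13 must be reconciled. Recruitment has stopped, so this corrects the record and does not change sampling.

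The cost is a few lines of SAP text and at most one rerun, with no new subjects or procedures. The statistical price is that about 1% to 9% of AUC is left to extrapolation if the half-life is 3 to 6 h, and more if it is longer (about half at 24 h).

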- 19. CR or PR should be confirmed not earlier than 28 days from the initial response scan, as per international working group criteria; see Section 14.4.3
- 20. Survival Follow-Up via telephone, email or other form of communication, every 6 months. Following Protocol Amendment 7, survival follow-up should only be conducted for subjects in an ACC cohort. Follow-up will continue until approximately 70% of subjects in the ACC cohorts have died.

See Section 5.4 for further details

Table 15 Time and Events for Part 3 (Active in all regions, except France)

Procedure	Screening		Da	ys 1-35		q3w	q8w	q26w	EOT (within
		Day 1	Day 8	Day 15	Day 22	(starting W6)	(starting W8)	(starting W26)	30 days post-
Screening		l				110,	110/	1120/	1401 4000)
Informed consent	Х								
Demography	Х								
Medical History	Х								
Inclusion/Exclusion Criteria	Х								
Disease Characteristics	Х								
Prior Therapy	Х								
Register Subject	Х								
Safety	•								
Full Physical Examination ¹	Х								Х

TMF-14123404

CONFIDENTIAL

204653

Procedure	Screening		Day	/s 1-35		q3w	q8w	q26w	EOT (within
Limited Physical Examination ¹	-	Х	Х	Х	Х	X	·	·	
ECOG Performance Status ²	Х	Х	Х	Х	Х	Х			Х
Vital Signs	Х	Х	Х	Х	Х	Х			Х
12-lead ECG	Х	PK ³		PK ³			Х		Х
DEXA Bone Densitometry	X4						Х		X ⁵
Pregnancy test (Females of childbearing potential only; screening test must be within 7 days prior to first dose)	х				Х	Х			Х
FSH/Estradiol (Only in women of non- childbearing potential)	х								
HIV, HbsAg, HCV Antibody Screening ⁶	Х								
Routine Clinical Laboratory Assessments ⁷	Х	Х	Х	Х	Х	Х			Х
Folate and selected vitamins ⁷	Х				Х		Х		Х
Ophthalmic Assessment ⁸	Х							Х	Х
Study Treatment									
Administer GSK33265959			←=====		==Daily Dosing=	===========	====→		
Administer Pembrolizumab				Х		Х			
Vision Symptom Review ¹⁰	Х	Х	Х	Х	Х	Х			Х
AE Review			Co	ntinuous from the	start of study tre	atment until th	e follow-up co	ntact	
SAE Review			Continuous	from signing of in	formed consent	until the follow	-up contact		
Concomitant Medication Review				Continuous from	signing of infor	med consent			
Pharmacokinetics (PK), Pharmacodynami	cs (PD) & Pharr	nacogenomics	s (PGx)						
PK Plasma ¹¹		Х		Х			Х		
Pembrolizumab PK ¹²				Х	Х	X (Q6W starting W6)			х
Pembrolizumab Immunogenicity ¹³				Х		X (Q6W starting			Х

TMF-14123404

CONFIDENTIAL

Procedure	Screening		Day	ys 1-35	q3w	q8w	q26w	EOT (within
					W6)			
Tumor Biopsy (archival) for p53 status	Х							
Tumor Biopsy (fresh) for p53 and PD ¹⁴	Х			Х				Х
Plasma (circulating biomarkers) ¹⁵		Х		Х		Х		
Whole blood (PAX tube for biomarker		v		v		v		
analysis, e.g., mRNA) ¹⁵		~		^		^		
PGx Sample (Blood) ¹⁶	Х							
Efficacy								
CT chest/abdomen/pelvis (see Section	v					V 18		V 19
8.2.1 and Section 8.7.1) ¹⁷	^					^ ¹⁰		A ¹⁰
MRI Brain ²⁰	Х							

NOTE: for visit windows, please refer to Section 8.2.2.

- 1. See Section 8.3.1 for components of full and limited physical examinations
- 2. See Section 14.3 for definition of ECOG performance status
- 3. On serial PK days (Day 1 and Day 15), ECGs will be obtained at or about the time of PK sample collection, as described in the SRM. On other days, ECGs will be obtained pre-dose
- 4. If possible, DEXA to be performed on same machine for particular subject
- 5. Only if EOT is > 8 weeks from prior DEXA
- 6. If test performed within 3 months prior to first dose of study treatment, testing at screening may not be required. Discuss with Medical Monitor if unclear.
- 7. Refer to Section 8.3.5 (Table 16) for complete listing of protocol-required laboratory assessments. Folate and selected vitamins to be drawn at Screening, Day 22, Week 8, every 8 weeks thereafter and at EOT. If a subject's folate or selected vitamins result(s) remain borderline or low at EOT visit, further testing may be requested until no longer deemed necessary in the opinion of the Investigator and Medical Monitor.
- 8. Refer to Section 8.3.7 for description of components of ocular assessment. If a subject's ocular result(s) remain abnormal at EOT visit, further testing may be requested until no longer deemed necessary in the opinion of the Investigator and Medical Monitor.
- 9. On serial PK days (Day 1 and Day 15), subjects should fast from 8 hours prior to dose until 2 hours after dose. On all other days, GSK3326595 should be administered on an empty stomach at approximately the same time of day (± 4 h), with no food for 1 hour before and 2 hours after each dose
- 10. At each visit, the investigator should specifically ask the subject about any changes in vision since their last visit/contact (Section 9.2.2). The investigator should document the response, consider if there are any reported events which meet the definition of an AE or SAEs, and intervene as clinically appropriate following discussion with the Medical Monitor if necessary.
- 11. GSK3326595 Plasma PK samples on Day 1 will be collected at Predose (within 1 hour prior to dosing), 30m±5m, 1h±5m, 2h±5m, 4h±10m, 6h±10m, 8h±15m, 12h±2h, 24h±2h (Day 2 prior to next dose) post dose. Additional PK samples will be collected at the following time points: Day 15, within 1 hr before dosing and between 1 and 3 hrs post dose, and between 5-8 hrs post dose. At subsequent scheduled visits, PK should be collected within 1 hr before dosing.
- 12. Pembrolizumab PK samples on Day 15 will be collected predose (within 1 hour prior to dosing), postdose (≤30 min after end of infusion) and 24h±2 h after the start of infusion. For D22, Pembrolizumab PK sample to be collected any time during the visit. At all other visits, predose PK samples will be collected (within 1 hour prior to

TMF-14123404

CONFIDENTIAL

dosing).

- 13. Pembrolizumab samples for immunogenicity will be collected at predose for all visits.
- 14. Refer to Section 8.2.1 for discussion of baseline biopsies. A fresh screening biopsy is required, even if there is archival tissue available, and should be taken within 14 days prior to the first dose. Paired biopsy to be taken on Day 15 prior to pembrolizumab administration, after 14 days of GSK3326595 dosing. EOT biopsy to be obtained as able for all subjects. The fresh biopsy will be used to determine p53 status if no archival sample is available.
- 15. Plasma and whole blood samples for biomarker analysis will be collected Day 1 (pre-dose) and 6h post-dose (±3 h) for all on-treatment samples. Plasma samples for circulating biomarkers to be collected as per the SoA until Week 24 only.
- 16. Informed consent for optional sub-studies (e.g. genetics research) must be obtained before collecting any samples. Appendix 8 describes requirements for genetic research
- 17. CT should be performed with oral and IV contrast. CR or PR should be confirmed not earlier than 28 days from the initial response scan, as per RECIST 1.1 criteria; see Section 14.4.1
- 18. After the fourth scheduled scan for disease assessment, scan frequencies are reduced. See Section 8.2.2 for details.
- 19. Repeat scans required at EOT visit only if the last radiographic assessment was more than 8 weeks prior to the subject's withdrawal from study and progressive disease has not been documented
- 20. MRI brain required at screening and then as clinically indicated thereafter; subjects with untreated CNS lesions should have brain MRI performed at each disease assessment. If MRI is contraindicated for an individual subject, then an equivalent study (e.g., contrast-enhanced MRI of the head) may be performed instead

